14.7 Potential risk of Progressive Multifocal Leukoencephalopathy (PML)

Cases of PML occurred in patients treated with anti-CD 20 including obinutuzumab. PML is a destructive infection of oligodendrocytes of the Central Nervous System (CNS) white matter, leading to neurologic deficits associated with demyelination. Death of oligodendrocytes leads to focal loss of myelin and dysfunction of associated myelinated tracts involving the cerebral hemispheres, cerebellum, or brainstem.

The symptoms of PML are unspecific, appear gradually, and can vary depending on the location of brain lesions. Motor involvement with corticospinal tract findings, sensory involvement, cerebellar deficits, and visual field defects are common. Some syndromes regarded as "cortical" (e.g., aphasia or visual-spatial disorientation) occur because the pathology of PML is typically immediately subcortical in the white matter, undermining the cortex referable to the clinical syndrome.

In this context, a clinical neurological examination must be performed at each clinical examination planned in the study protocol during treatment and follow up periods. The LYSARC would like to focus on the importance of investigating further any unexplained neurological symptoms identified during the study.

The diagnosis of PML should be considered in any patient presenting with new-onset neurological manifestations or symptoms like weakness or paralysis, vision loss, impaired speech and cognitive deterioration, and not only to the possible cerebral relapse of patient lymphoma. Exploration of PML includes, but is not limited to, consultation with a neurologist, brain MRI and a lumbar puncture for JC virus detection by PCR in Cerebrospinal Fluid (CSF). PCR analysis of CSF for JC virus is the best test to confirm PML (the other parameters of spinal fluid are typically normal).

The therapy with obinutuzumab should be discontinued during the investigations of a potential PML and permanently stopped if the diagnosis of PML is confirmed. Discontinuation or reduction of any concomitant chemotherapy or immunosuppressive therapy should also be considered. The patient should be referred to a neurologist for the adequate monitoring and treatment of PML.

15 GENERAL STATISTICAL CONSIDERATIONS

15.1 Endpoints

15.1.1 *Primary endpoint*

The primary endpoint is the Molecular residual disease (MRD) negativity after induction. Assessment of MRD will be based on molecular level in BM according to EU MCL network guidelines. Patient without MRD assessment (due to whatever reason) will be considered as MRD positive.

This endpoint will be analyzed on efficacy set (ES) and also on modified efficacy set (mES) as sensitivity analysis.

15.1.2 Secondary endpoints

15.1.2.1 Efficacy endpoints

Response according to Cheson 99 and overall response rate after 3 years of maintenance

Response after 3 years of maintenance will be evaluated. Assessment of response will be based on the International Workshop to Standardize Response criteria for NHL (Criteria for evaluation of response in Non-Hodgkin's lymphoma (Cheson, 1999) See Appendix 8). Patient without response assessment (due to whatever reason) will be considered as non-responder. Overall (CR/PR) response rate will be also presented.

An additional analysis will be performed considering as non-responders all patients who relapsed or died during treatment phase even if they were prematurely treatment discontinued as responder during treatment phase.

This endpoint will be analyzed on efficacy set (ES) and on safety set (SS).

PET result after 3 years of maintenance

PET result after 3 years of maintenance will be evaluated. Assessment of PET will be based on Lugano 2014 criteria (according to Cheson & Al. J. Clinic Oncol 2015). See Appendix 9 (Reponse criteria for lymphoma – Lugano classification).

This endpoint will be analyzed on efficacy set (ES) and on safety set (SS).

MRD after 3 years of maintenance and after maintenance “on demand”

Molecular residual disease (MRD) after 3 years of maintenance and after maintenance “on demand” will be evaluated. Assessment of MRD will be based on molecular level in BM according to EU MCL network guidelines. Patient without MRD assessment (due to whatever reason) will be considered as MRD positive.

This endpoint will be analyzed on efficacy set (ES).

PFS

PFS is defined as the time from inclusion into the study to the first observation of documented disease progression or death due to any cause. If a subject has not progressed or died, PFS will be censored at the time of last visit with adequate assessment.

This endpoint will be analyzed on efficacy set (ES) and on safety set (SS).

OS

Overall survival will be measured from the date of inclusion to the date of death from any cause. Alive patients will be censored at their last contact date.

This endpoint will be analyzed on efficacy set (ES) and on safety set (SS).

Stem cell collection failure

Stem cell collection failure will be evaluated after induction.

This endpoint will be analyzed on efficacy set (ES) and on safety set (SS).

Duration of MRD negativity

Duration of MRD negativity is defined as the time from the date of attainment the first negative MRD to the date of positive MRD. Duration of MRD negativity would be assessed for patients with at least one MRD negativity and as survival endpoint. For patients achieving a negative MRD but who have not positive MRD or not MRD assessment at the time of analysis, duration of MRD negativity will be censored on the date of last MRD assessment.

This endpoint will be analyzed on efficacy set (ES).

15.1.2.2 Safety endpoints

Summary of study drug administration including treatment duration and average dose will be displayed.

Number, frequency, reasons for premature treatment discontinuation and study discontinuation will be summarized.

Adverse events, clinical laboratory measurements will be described.

AEs will be classified using the latest version of Medical Dictionary for Drug Regulatory Activities (MedDRA) coding system at the time of database lock. The severity of the toxicities will be graded according to the National Cancer Institute (NCI) Common Terminology Criteria for Adverse Events (CTCAE) whenever possible. Subsets of AEs to be summarized include serious, NCI CTCAE grade severities, suspected treatment-related, and events that resulted in withdrawal of investigational product. The most severe grade of each preferred term for a patient will be utilized for summaries of adverse events by NCI CTCAE grade.

All AEs and SAEs will be described by system organ class and preferred term (a patient having the same event more than once will be counted only once) by period. Focus on AEs leading to death, AEs leading to discontinuation from treatment and AEs of special interest (i.e Tumor Lysis Syndrom) will also be displayed in a separate table and listing.

All deaths will be listed and summarized by cause of death and narratives of death will be also presented.

This endpoint will be performed on safety set (SS)

15.1.3 Exploratory endpoints

Baseline prognostic factors on PFS and OS

A dedicated analysis on survival (PFS/OS) will be performed in order to determined baseline prognostic factors. The implemented method will take into account the specificities of on-demand treatment during the second maintenance period.

15.2 Sample size calculation and tested hypothesis

Hypothesis:

We expect to have an increase of 15% of the MRD negativity in bone marrow (BM) rate for patients treated with GA-DHAP.

Based on the interim results of LYMA presented at ASH 2014, the MRD negativity rate were 65% (Legouill, ASH 2014). Nevertheless, in the LYMA study, the MRD has been assessed after 4 cycles of DHAP only for patient that completed the 4 cycles. Therefore this rate does not take into account the rate of patients who progressed on treatment or took R-CHOP because of insufficient response. If we take into account these patients considering them as non responder patients and based on the LYSA/LYSARC experience, then the MRD negativity rate of all patients in the LYMA may be around 55%. Considering that these patients will also be included in the LyMa101 we have to take into account a rate of 55% of MRD negativity instead of 65% in the sample size calculation.

The hypotheses are as follows:

- Experimental treatment will be considered ineffective if the MRD negativity in BM after the 4 cycles or at treatment discontinuation (at a molecular level) proportion is $\leq 55\%$ (P_0)
- Experimental treatment will be considered effective if the MRD negativity in BM after the 4 cycles or at treatment discontinuation (at a molecular level) proportion $\geq 70\%$ (P_1)
- α risk of 0.05 and β of 0.20
- one-sided test

Patients will be considered as MRD positive if the patient has no MRD assessment due to whatever the reason.

Sample Size:

A total of 70 evaluable patients will be required for this study. Assuming that some included patients will not receive the treatment or will not be informative for MRD in bone marrow and/or blood at baseline, enrollement will be done until 70 patients are evaluable. For this purpose, about 83 patients should be enrolling (15% drop-out).

Sample size calculation was performed using an exact single-stage phase II design with East 5.4 (A'Hern RP. Sample size tables for exact single-stage phase II designs. Stat Med. 2001. 20(6):859-66).

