Statistical consideration	
The primary endpoint of this phase II study is the MRD in bone marrow according to EU MCL network guidelines after the 4 cycles or at treatment discontinuation whatever reason, of GA-DHAP.
 
Analysis sets
 
The Efficacy set will include all patients having signed their informed consent, received at least one dose of the IMP and with an informative MRD (characterized tumoral clone) in bone marrow (BM) and/or blood at baseline.
 
The Safety set will include all patients having signed their informed consent and received at least one dose of the IMP.
 
The analysis of the primary criterion will be performed on the Efficacy set and also on modified Efficacy Set as sensitivity analysis.
 
Secondary endpoints (including safety endpoints) will be performed on Efficacy and Safety sets.

Sample Size CalculationHypothesis:

We expect to have an increase of 15% of the MRD negativity in bone marrow for patients treated with GA-DHAP.

Based on the interim results of LYMA presented at ASH 2014, the MRD negativity rate was 65% (Legouill, ASH 2014). Nevertheless, in the LYMA study, the MRD has been assessed after 4 cycles of DHAP only for patient that completed the 4 cycles. Therefore this rate does not take into account the rate of patients who progressed on treatment or took R-CHOP because of insufficient response. If we take into account these patients considering them as non responder patients and based on the LYSA/LYSARC experience, then the MRD negativity rate of all patients in the LYMA may be around 55%. Considering that these patients will also be included in the LyMa101 we have to take into account a rate of 55% of MRD negativity instead of 65% in the sample size calculation.

The hypotheses are as follows:

- Experimental treatment will be considered ineffective if the MRD negativity in BM after the 4 cycles or at treatment discontinuation proportion is $\leq 55\%$ (P0)
- Experimental treatment will be considered effective if the MRD negativity in BM after the 4 cycles or at treatment discontinuation proportion $\geq 70\%$ (P1)
- α risk of 0.05 and β of 0.20
- one-sided test

Patients will be considered as MRD positive if the patient has no MRD assessment after the 4 cycles or at treatment discontinuation due to whatever reason.

Sample Size:

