15.5 Time of analyses

Given the fact that primary endpoint is prematurely determined in study treatment period, 2 types of analysis will be performed:

- Primary criterion analysis

- Final analysis

Primary criterion analysis:

This analysis will be performed once all patients included in efficacy set (70 patients) have completed the 4 cycles of treatment or treatment discontinued prior to cycle 4 and will consist of analyzing:

- Primary criterion : MRD negativity in BM rate after the 4 cycles or at treatment discontinuation of GA-DHAP
- Treatment exposure
- Stem cell collection failure
- Secondary safety endpoints

Among the 70 evaluable patients, if 46 patients or more have a MRD negativity after the 4 cycles or at treatment discontinuation the treatment will be considered as sufficiently effective and further investigations (another trial) will have to be foreseen.

Final analysis:

This analysis will be performed when all included patients will undergo the end of treatment visit (at end of maintenance “on demand” period or at treatment discontinuation) and will consist of the whole statistical analyses.

At this time all secondary and exploratory endpoints will be analyzed.

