## 4 STATISTICAL CONSIDERATIONS

### 4.1 Sample size calculation

#### Hypothesis:

We expect to have an increase of 15% of the MRD negativity in bone marrow (BM) rate for patients treated with GA-DHAP.

Based on the interim results of LYMA presented at ASH 2014, the MRD negativity rate were 65% (Legouill, ASH 2014). Nevertheless, in the LYMA study, the MRD has been assessed after 4 cycles of DHAP only for patient that completed the 4 cycles. Therefore this rate does not take into account the rate of patients who progressed on treatment or took R-CHOP because of insufficient response. If we take into account these patients considering them as non responder patients and based on the LYSA/LYSARC experience, then the MRD negativity rate of all patients in the LYMA may be around 55%. Considering that these patients will also be included in the LyMa101 we have to take into account a rate of 55% of MRD negativity instead of 65% in the sample size calculation.

The hypotheses are as follows:

- Experimental treatment will be considered ineffective if the MRD negativity in BM after the 4 cycles or at treatment discontinuation (at a molecular level) proportion is  $\leq 55\%$  ( $P_0$ )
- Experimental treatment will be considered effective if the MRD negativity in BM after the 4 cycles or at treatment discontinuation (at a molecular level) proportion  $\geq 70\%$  ( $P_1$ )
- $\alpha$  risk of 0.05 and  $\beta$  of 0.20
- one-sided test

Patients will be considered as MRD positive if the patient has no MRD assessment due to whatever the reason.

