### 4.2 Primary criterion analysis

This analysis will be performed once all patients included in efficacy set (70 patients) have completed the 4 cycles of treatment or treatment discontinued prior to cycle 4 and will consist of analyzing:

- Primary criterion : MRD negativity in BM rate after the 4 cycles or at treatment discontinuation of GA-DHAP
- Treatment exposure
- Stem cell collection failure
- Secondary safety endpoints

Among the 70 evaluable patients, if 46 patients or more have a MRD negativity after the 4 cycles or at treatment discontinuation the treatment will be considered as sufficiently effective and further investigations (another trial) will have to be foreseen.

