## 5.7 Efficacy Analysis

### 5.7.1 Primary efficacy analysis

#### 5.7.1.1 Main analysis

**Table 5.7.1.1-1 MRD results on BM after induction or at treatment discontinuation – Efficacy Set**

	ddPCR N=XX	Q-PCR N=XX
MRD after induction		
Negative	XX (XX.XX%)	XX (XX.XX%)
Positive	XX (XX.XX%)	XX (XX.XX%)
Positive < 10E-04	XX (XX.XX%)	XX (XX.XX%)
Missing	XX (XX.XX%)	XX (XX.XX%)
MRD negativity rate*		
Negative	XX (XX.XX%)	XX (XX.XX%)
IC 95%	[XX.XX% - XX.X%]	[XX.XX% - XX.X%]

\* Patients without MRD assessment are considered as Positive MRD

**Listing 5.7.1-1 Patients with missing MRD results on BM after induction or at treatment discontinuation – Efficacy Set (XX patients)**

Patient identification number	Inclusion date	Last period	Patient suitable for MRD monitoring	MRD after Induction	
				Interpretation on PB	Interpretation on BM
XXXXX	XX/XX/XX	XX	XX	XX	XX

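### The 55% null counts LyMa progressors and R-CHOP switchers as failures, but the 46-of-70 rule lets such patients count as successes

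*Protocol*

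**What the plan says.** **Benchmark** (Protocol Synopsis and 15.2; SAP 4.1). The 65% from LyMa covers only patients who completed four cycles. For those who progressed or were given R-CHOP for insufficient response, the text says "If we take into account these patients considering them as non responder patients", and concludes that "the MRD negativity rate of all patients in the LYMA may be around 55" per cent. SAP 4.1 gives the reason: "Considering that these patients will also be included in the LyMa101".

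**Endpoint and decision rule.** The Protocol Synopsis sets the marrow assessment after four cycles or "at treatment discontinuation whatever reason, of GA-DHAP". Protocol 15.5 names the primary criterion as "MRD negativity in BM rate after the 4 cycles or at treatment discontinuation of GA-DHAP". SAP 4.2 declares the treatment sufficiently effective "if 46 patients or more have a MRD negativity after the 4 cycles or at treatment discontinuation".

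**The only imputation.** Protocol 15.1.1 states: "Patient without MRD assessment (due to whatever reason) will be considered as MRD positive". The footnote to SAP Table 5.7.1.1-1 repeats it: "Patients without MRD assessment are considered as Positive MRD".

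**Who reaches the discontinuation sample.** Protocol 13.1 lists progression and the start of other anti-neoplastic therapy among the reasons to stop study treatment. Protocol 10.4.1 withdraws from study treatment anyone who needs a prohibited anticancer therapy. Protocol 9.9 and 11.3.2.1 call for marrow at premature discontinuation.

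**The concern.** The stated purpose of lowering the null is to compare like with like: the same kinds of patient are in both trials, so both should be counted. They are counted differently. In the 55%, a progressor or switcher can only be a failure. In LyMa101, the same patient is classified by the marrow result at discontinuation, and a negative result adds to the 46. Neither document scores progression or a change of therapy as MRD-positive for the primary endpoint.

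Protocol 5.4 says the results will be compared with LyMa, and the go decision is a single count against the null. If the null was built under one scoring rule and the count under another, the nominal 5% does not describe the risk of declaring success for a drug no better than the LyMa regimen. A reader of a result near 46/70 could not separate the drug from the scoring.

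**Working it through.** **1. Reproduce the design.** Inputs from Protocol 15.2 and 15.5: n = 70, success at 46 or more, P0 = 0.55, P1 = 0.70, one-sided alpha 0.05, beta 0.20.

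P(X ≥ 46 | p) = Σ C(70, x) pˣ (1 − p)⁷⁰⁻ˣ, summed over x = 46 to 70.

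- p = 0.55: 0.0452 (type I error)
- p = 0.70: 0.8201 (power)
- 70 / 0.85 = 82.4, rounded up to 83 enrolled

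The plan's figures reproduce, and 70 is the smallest n that meets both limits. There is little slack: a cut-off of 47 would give alpha 0.0262 and power 0.746, below the 0.80 required.

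**2. Effect of the mismatch alone.** If k progressors or switchers per 70 are marrow-negative at discontinuation, the null on the trial's own scoring is 0.55 + k/70.

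- k = 1: p = 0.5643, alpha 0.0730
- k = 2: p = 0.5786, alpha 0.1124

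**3. Effect of the approximate 55%.** A null of 0.54 gives alpha 0.0314 and 0.56 gives 0.0635. With one extra success per 70 these become 0.0525 and 0.0992.

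**4. The offset.** One would-be negative per 70 lost to a missing marrow gives p = 0.55 − 1/70 = 0.5357 and alpha 0.0267.

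**5. Both together.** The documents do not give the share of progressors and switchers. If the whole gap from 65% to 55% is due to them (an inference), the share is s = 1 − 0.55/0.65 = 0.154, or about 10.8 of 70. Let q be the proportion of them who are marrow-negative and m the proportion of completers with missing marrow; both are assumptions. Then null = 0.55(1 − m) + s·q, and alpha for 46/70 is:

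| | q = 5% | q = 10% | q = 20% |
|---|---|---|---|
| m = 0 | 5.9% | 7.6% | 12.0% |
| m = 5% | 2.2% | 2.9% | 5.1% |
| m = 8% | 1.1% | 1.5% | 2.8% |

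**6. After aligning the scoring.** The s·q term drops out. Alpha is 4.5% at m = 0 and 1.6% at m = 5%. Power stays at 82.0% if the 70% target is on the same scoring as the 55%. If 70% was meant on the scoring as written, power falls as follows:

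- 0.70 − 1/70: 74.3%
- 0.70 − 2/70: 65.3%
- 0.70 − s·q: 78.0%, 73.7% and 63.8% for q = 5%, 10% and 20%

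**7. Does anything else in the plan close the gap?**

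- The modified Efficacy Set (Protocol 15.3, SAP 4.4.3) also takes the discontinuation result, so that sensitivity analysis repeats the mismatch.
- Protocol 9.11 bases progression on CT and not on MRD, so the definitions allow a marrow-negative progressor.
- Protocol 9.9 puts the discontinuation evaluation within 28 days and Protocol 13.1 within 28 weeks. The two must be reconciled; as they stand, a sample could follow other therapy.

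**The case against.** The strongest reply is that no net error is shown. Both documents state the null on the trial's own endpoint, and against 55% on that endpoint the exact error is 4.5%. The missing-as-positive rule works against the drug: with 5% of completers missing, two of the three values in the table are below 5%. The 15.4% share is inferred and probably too high for the patients concerned here. Protocol 10.2.2 takes partial response and stable disease to transplant, and no R-CHOP switch is described. At half that share, alpha with no missing marrow is 5.2%, 5.9% and 7.6% for q = 5%, 10% and 20%.

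The value of q has no direct source either. Protocol 11.3.1 says relapse is strongly associated with MRD positivity and cites 13% blood-negative. That figure concerns blood at relapse, not marrow during induction. Using it anyway with the full share gives 8.7% with no marrow missing, 5.1% with 3% missing and about 3.5% with 5% missing. Success leads only to another trial, and the primary analysis has probably been done.

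Much of this stands. The net direction is unknown, and a primary endpoint should not be rescored after its results are known. But the reply does not remove the mismatch. A test can be valid against 55% while 55% is the wrong figure for LyMa patients scored as this trial scores its own. Two unquantified errors in opposite directions do not make a calibrated comparison.

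**Conclusion.** The plan is wrong as written on this point. The sample size, cut-off and enrolment arithmetic are correct; the fault is that benchmark and trial score the same kind of patient differently, in the drug's favour.

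Taken alone, a single marrow-negative progressor or switcher per 70 is enough to push the type I error past the nominal 5%. The effect is nil if all such patients are marrow-positive or unsampled. Whether the overall error is above or below 5% cannot be determined from the documents. It depends on three things they do not give: how many such patients there are, how many are marrow-negative, and how many completers lack a marrow result. The softness of the 55% adds to this. The case therefore rests on the inconsistency and the small margin, not on a demonstrated inflation.

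**What to change.** In Protocol 15.1.1 and 15.2 and SAP 3.2.1 and 4.2, define the scoring for the primary analysis and the 46/70 decision. Count as MRD-positive any patient who, before the post-induction marrow sample, either progresses, or stops GA-DHAP for insufficient response and starts non-protocol anti-lymphoma therapy, whatever the marrow shows at discontinuation. P0, n and the cut-off then stand. Report the current scoring as a sensitivity analysis. The plan already has a rule of this kind for clinical response, as an additional analysis (Protocol 15.1.2.1, SAP 3.2.2.1).

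The primary criterion analysis was planned for Q1 2019 and SAP version 2.0 is dated October 2024. If that analysis is done, leave it unchanged, present the aligned scoring beside it, and say whether the 46/70 conclusion holds under both.

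State what this does not resolve:

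- Insufficient responders who stay on protocol here but might have been counted as failures in LyMa. One marrow-negative patient of this kind per 70, with null 0.55(1 − m) + 1/70, gives alpha 7.3% at m = 0, 4.2% at m = 3% and 2.8% at m = 5%.
- Patients who stop for other reasons, whose handling in the 55% is not described.
- The assay behind the 65%, since SAP Table 5.7.1.1-1 reports both ddPCR and Q-PCR.

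The change removes one source of inflation; it does not guarantee a conservative test.

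The cost is SAP wording, one derived variable and one table, with no new patients or samples. The discontinuation reasons in SAP 5.2.1 will not isolate switchers, who may be coded as protocol deviation or physician decision. The dated non-study treatment records in SAP 5.12 and a case review are also needed. The reported negativity rate may be lower, with the possible power loss in step 6 of the working.
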